The U-s National Athletic Injury Reporting System (NAIRS) divides overuse injuries into the following categories:

- a) Undetectable – where the athlete does not stop their athletic activities,
- b) Minor leaving 1-7 days of sports activity
- c) Moderate: from 8 to 21 days of abandonment of activities and
- d) Major: more than 21 days of loss of activities and serious injuries, resulting in permanent disability.

TREATMENT OF KNEE OVERUSE SYNDROME:

There is no specific treatment guideline for most conditions caused by knee overuse. It is essential to have an adequate diagnosis of osteoarthritis at an early stage to incorporate the most appropriate treatment. The most recommended treatment for early osteoarthritis, includes weight loss, physical therapy, non-steroidal anti-inflammatory drugs, nutraceutical supplements, topical treatments, and steroid injections. In knee overuse syndrome, starting with a decrease in overload, correcting gait abnormalities, improving training techniques, adding strengthening and stretching exercises, as well as adapting the use of footwear and adding physical therapies with ice, have resulted effective methods as first line treatment.

NON-SURGICAL

The first line of treatment in early osteoarthritis of the knee caused by overuse in sports should be given conservatively and without surgery. The main objective of this treatment is to delay arthroplasty through a protocol that includes non-steroidal anti-inflammatory drugs, joint injections, as well as general measures of weight loss following a series of low-impact exercises. Physical therapy has an important role in the treatment of early osteoarthritis in athletes, stretching the extensor and abductor muscles of the knee can reduce pain and improve function. Cold therapy can also decrease the level of prostaglandins in synovial tissue resulting in decreased inflammation, reducing atherogenic muscle inhibition and facilitating vastus medialis motor neuron activity. Cryotherapy may allow more effective strengthening of the quadriceps in patients with knee joint abnormality; therefore, despite the current lack of clear research evidence, cryotherapy is recommended as a mainstay of conservative treatment in physiotherapy.

NON-STEROID ANTI-INFLAMMATORY AGENTS

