Composition: Each 1 ml contains: hyaluronic acid 20 mg, Sorbitol 40 mg, phosphate buffered solution 1ml. Synolis VA contains a 2 ml siringe of viscoelastic solution.

Contraindications.

Synolis VA should not be used in:

- Patients known to be hypersensitive to hyaluronic acid or sorbitol.
- Pregnant lactating patients
- Minors
- Skin disease or infection at the level of the application site.

CLINICAL EVALUATION

The knee injury and Osteoarthritis Outcome Score (KOOS) is a new, well-designed, and simple self-administered instrument developed to assess short, and long-term symptoms and function in patients with knee injuries and osteoarthritis. It has good evidence of reliability, validity, and responsiveness in different populations with different pathologies, injury duration, ages, and activity levels. The KOOS scale has been shown to be very effective in Young and active patients; it is intended to be used in short and long-time intervals; to assess week-to-week changes induced by treatment (medication, surgery, physical therapy). All items were scored from 0 to 4, and each of the five scores was calculated as the sum of the included items; scores are then converted to a scale of 0-100, where zero represented extreme knee problems and 100 represented no knee injury, this can be represented as a percentage.

The INTERNATIONAL KNEE DOCUMENTATION COMMITTEE IKDC, is a patient-oriented score to qualify symptoms and functions related to the activity of daily living; evaluates knee injuries and categorizes them into subjective variables, symptoms, ranges of motion and ligamentous exploration, which is subcategorized into normal, almost normal, abnormal and severely abnormal, the objective of this scale is to provide the physician with information on patient satisfaction and their knee. Points on the *Subjective Knee Assessment Form* are calculated by adding the points for the individual items, and then transforming the points on a scale from 0 to 100. The transformed points are interpreted as a measure of the ability to function, with higher points representing higher levels of functioning and lower levels of symptoms. One hundred points are interpreted to mean that there is no limitation in activities of daily living or sports activities, and the absence of symptoms.

Justification and Statement of the Problem

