Affected Knee	Anatomic Knee side	Left	Qualitative	Physical Exploration	Left

		Right	Nominal		Right
Athlete	Person who practice any type of sport	Social Amateur Professional	Qualitative Nominal	Interview	Have a sports activity for more than 3 months, 3 times a week over 60 minutes per session
Score KOOS	Scores that evaluate functional and osteoarthritis around the knee	Symptoms Joint Stiffness Pain Regular activities Sports activities Quality of life	Quantitative Discrete	Interview Physical Exam	Percentage 0-100%
Score IKDC	International Knee Documentation Committee	Symptoms Regular Activities Sports Activities	Quantitative Discrete	Interview Physical exam	Percentage 0-100%
Visco supplementation	Intraarticular joint injection of high weight molecular hyaluronic acid with sorbitol	Mono dose Multi dose	Qualitative Nominal	Hyaluronic acid 2ml plus sorbitol 2 dose per knee	Yes = Knee joint infiltration No= Did not apply
Training sports technique	Coaching for adequate techniques of certain sports	Manual technique Instrumented	Qualitative Nominal	Personalized coaching techniques	Achievement survey

	activities			Or Information brochure	
--	------------	--	--	----------------------------	--

Research Universe

General Population who does sports activities and have knee overuse syndrome between June of 2022 and October 2022.

Sample Size

It will be a non-probability sampling where will be chosen participants who meet selection criteria over the enrolling time which will be for 5 months. The lower limit will be 60 participants and the higher limit will be 120 participants.

Sample size formula: $n(\text{sample})$, z (confidence level), p (probability to occur the studied event), q (probability to didn't occur the studied event) and e (maximum accepted estimated error)

$$Z^2 * p*q$$

$$n = \frac{Z^2 * p*q}{e^2}$$

Study Design

Research enrolling and diffusion will be initiated after authorization of the ethics and investigation committee. All participants with knee pain related to sports will be accepted for a physical evaluation. All participants will be interviewed about physical activities, sports, injuries, and knee pain. Once they have been categorized as athletes with knee overuse pain syndrome and have met the selection criteria, then will be invited to the research. For this, the participants must be agreed and sign the informed consent Appendix 1 and 2.

Before treatment Group

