To participants who initiate the study research will be applied the KOOS and IKDC scores, the results will be recorder in the collection data sheet. Appendix 2. Participants will be explored by physical exam focus on knee pathology, and also an echography knee scan

looking for non-overuse pain injuries. Coaching for sports activities will be explained for each patient in order to improve its own training techniques adding stretching exercises for previous and after training.

After treatment Group

After KOOS and IKDC scores were recorded two doses of Hyaluronic Acid plus sorbitol will be applied. Technique: On the examination table, the patient will lie down at supine position and the area of the knees to be infiltrated will be discovered. Asepsis of the knee region will be performed using an iodine and alcohol solution, the remaining synovial fluid in the joint will be extracted with a 10cc syringe then 4 milliliters of 80 mg of hyaluronic acid plus 160 mg of sorbitol will be applied (Synolis VA Aptissen S. A.) at the sub quadriceps level with a 22G x 32mm sterile needle. At the end of the infiltration, the needle will be removed, and the injection site will be covered with a small sticky-band, which can be thrown away after 20 minutes. It will be recommended to not make any kind of sports activity following the next 72 hours and apply ice therapy 3 times per day for over 20 minutes. Scores recorded data will be made at 15 days, then at 3 and 6 months.

Once the enrolling phase of the trial is concluded, statistical analysis will be made with Excel Office software for Windows, IBM SPSS and Prism.

Statistical analysis

Recorded data of the functional scores will be evaluated before and after treatment, also at 15 days, 3 and 6 months after hyaluronic acid supplementation.

Data analysis will be made by means standard deviation for numeric variables, also t-test for parametric and Wilcoxon Mann Whitney for non-parametric variables, a standard error of 95% is allowed. Differences in time will be calculated and group compared by Anova test. Variable correlation and association measures with relative risk and attributable risk with Fisher's test will be made with a confidence interval of 95%.

Ethical Implications

This research project will be developed after approval of the ethics and research Institutional committee.

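### With one cohort, shared co-interventions and no comparator, the before/after change in KOOS and IKDC cannot support the product efficacy that the protocol claims

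*Combined protocol and SAP*

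**What the plan says.** All references are to the combined protocol and SAP.

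- **Design.** Methods, Study Design, describes a single prospective cohort. One specific objective is a comparison of results before and after treatment. The subsections Before treatment Group and After treatment Group describe the same people at two stages.
- **What participants get.** Under Before treatment Group, after the baseline scores: "Coaching for sports activities will be explained for each patient in order to improve its own training techniques adding stretching exercises". Under After treatment Group, as part of the injection technique: "the remaining synovial fluid in the joint will be extracted with a 10cc syringe". Participants are then recommended to "not make any kind of sports activity following the next 72 hours and apply ice therapy 3 times per day". On follow-up: "Scores recorded data will be made at 15 days, then at 3 and 6 months".
- **What is claimed.** The title speaks of effectiveness. The aim in the Abstract, the justification, the General Objective, the first specific objective and the data sheet in Appendix 3 speak of efficacy of the product. The Hypothesis and Null Hypothesis attribute good results, or their absence, to the infiltration.
- **What the protocol says of the co-interventions.** The section on treatment of knee overuse syndrome lists "improving training techniques, adding strengthening and stretching exercises" together with ice and other measures, and says that these "have resulted effective methods as first line treatment".
- **Outcome.** Clinical Evaluation describes KOOS as a "simple self-administered instrument developed to assess short, and long-term symptoms and function".
- **Analysis.** Statistical analysis names a t-test (not stated to be paired), Wilcoxon Mann Whitney, ANOVA across time and group, and relative and attributable risk. The Variables table codes viscosupplementation as "Yes = Knee joint infiltration No= Did not apply".

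**The concern.** The stated efficacy claim concerns one product, but the only planned evidence for it is change over time in people who all receive that product together with several other things. The protocol itself calls some of those other things effective. If the plan is followed as written, a significant improvement in KOOS or IKDC answers the efficacy objective and the hypothesis, although this design could produce the same result with no product effect. What is at stake is the conclusion the study may draw, not the usability of its data.

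**Working it through.** The plan gives no figure on this point to reproduce. The sample range of 60 to 120 does not bear on it. The check sets the sections side by side.

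**1. What lies between baseline and follow-up scores**

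| Component | Who | Rival to product efficacy? | Rival to the infiltration hypothesis? |
|---|---|---|---|
| Coaching and stretching | each participant | yes | yes |
| Extraction of joint fluid | part of the infiltration technique | yes | no, it belongs to the procedure |
| Sports pause and ice | recommended after infiltration | yes | yes, limited by timing (step 3) |
| Placebo response, no masking described | all | yes | yes, unless the effect of simply being injected is counted as infiltration |
| Symptoms that come and go (Diagnosis section) | all | yes | yes |

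The Abstract places the sports strategies after the injection. Before treatment Group places coaching after the baseline scores and before the injection. On either order it falls inside the comparison.

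**2. What the comparison can identify**

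Write the expected mean change, additively for simplicity, as

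E(D) = P + C + F + B + N

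where P is the product, C coaching, stretching, pause and ice, F fluid extraction, B placebo response and N natural course with regression to the mean. Only D is observed, so one equation has five unknowns. E(D) > 0 is compatible with P = 0. Sample size does not help: going from n = 60 to n = 120 multiplies the standard error of D by √(60/120) = 0.71 but leaves E(D) unchanged. A comparator sharing every term except P would isolate P, and none is defined.

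**3. How far the pause reaches**

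Count days from the infiltration session and assume that ice ends with the 72-hour pause. IKDC items with a stated recall look back 4 weeks (28 days); KOOS items with a stated recall look back one week.

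- Day 15, IKDC: 15 − 28 = −13, so the window includes the pause.
- Day 15, KOOS: 15 − 7 = day 8, after the pause.
- 3 months (about 90 days), IKDC: 90 − 28 = day 62, well after it. At 6 months the gap is larger.

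The pause can enter the recall period of the 15-day IKDC only. Coaching and stretching have no stated end.

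**4. Is a comparator implied anywhere?**

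Three items hint at one: the No category for viscosupplementation, ANOVA by group, and relative and attributable risk. No uninjected group is described. For injection as the exposure, relative risk is [a/(a+b)] / [c/(c+d)], with c + d the number uninjected. Here c + d = 0, so the ratio and the corresponding risk difference are undefined. Coaching may be personalised or a brochure (Variables), but contrasting those forms compares coaching among injected people, not injection with none.

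**5. Timing**

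Research Universe gives June to October 2022. October 2022 plus 6 months is about April 2023. The document is dated 01/12/2023, which follows planned enrolment whether read as January or December. On the December reading it also follows the last planned score.

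**The case against.** The strongest reply is that the design is disclosed. The protocol calls itself a cohort study, sets a before/after objective and asks in its research question only whether there is a difference. No rule in Statistical analysis turns a p-value into an efficacy verdict. This stands as a defence of the design and of the before/after objective, which can be met descriptively. It does not rescue the efficacy objectives or the hypotheses, because before/after change is the only feasible analysis offered for them.

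Other replies stand in part:

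- Fluid extraction belongs to the infiltration technique, so it does not compete with the hypothesis, only with the wording about the product.
- Coaching is explained rather than supervised and may be a brochure, so uptake is unknown. The achievement survey and the planned correlations offer a partial handle but create no comparator.
- The list of effective measures also includes load reduction, gait correction and footwear, and the Non-surgical section concedes a lack of clear research evidence for cryotherapy. The co-interventions are possible causes, not proven ones; possible is enough here.
- Selection sets no minimum score and requires pain for more than 3 months, so regression to the mean is not assured. Enrolment because of pain in a fluctuating condition still leaves it open.
- The Variables table lists interview and physical examination, and an assistant collects the scores. Neither masks anyone.
- A late rewrite of hypotheses can look retrospective. That is a reason to date it and state the analysis status, not to leave the claim in place.

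A reader might go further and infer a false-positive rate for the efficacy claim. The documents do not support one. It needs the non-product shift relative to the SD of change, which is not given. The enrolment limits are not the analysed numbers, because the elimination criteria remove participants without complete follow-up. And good results has no threshold, so a significant mean change is not rejection of the protocol's null.

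**Conclusion.** The concern holds for the claim, not for the design. As written, a before/after change in KOOS or IKDC cannot support efficacy of hyaluronic acid plus sorbitol, nor good results credited to the infiltration.

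No size is attached, because nothing in the documents fixes the non-product part of the change. The conclusion rests on two readings of the text: no comparator or masking is described anywhere, and every participant gets the co-interventions within the comparison window.

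Two stronger inferences should be resisted. The documents do not show that the product is ineffective or that coaching explains the improvement. Nor do they make a single-cohort study invalid: the safety objective and a descriptive account of change after the package remain sound.

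**What to change.** Keep the safety objective and the before/after objective. By dated amendment, stating whether scores had already been analysed:

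1. Replace product efficacy or effectiveness in the title, the aim, the justification, the objectives and the Appendix 3 data sheet with change from baseline in KOOS and IKDC after the combined package. Define the package as hyaluronic acid plus sorbitol with joint fluid extraction, coaching, stretching, and the recommended sports pause and ice.
2. Restate both hypotheses without attributing results to the infiltration. For example, null: the mean change from baseline in the score is zero; alternative: it is not zero; both for the package.
3. State in Statistical analysis that the comparison is within patient and that no causal efficacy claim for the product will be drawn from it.
4. Remove from that section the between-group ANOVA, relative risk and attributable risk as evidence of a product effect, since no uninjected group exists. Analysis of differences over time within participants can stay.

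The change needs no added patients, procedures or data and alters no clinical management. Its cost is a weaker but accurate claim and an amendment made after planned enrolment.

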RESEARCH PROTOCOL

Study title: Safety and effectiveness of hyaluronic acid and sorbitol with overuse knee pain in sportsmen

Protocol Reference ethics committee number: CEI/0504/PI./2022

ClinicalTrials.gov: NCT05450458

DATE: 01/12/2023

ABSTRACT

INTRODUCTION

KNEE OVERUSE KNEE SYNDROME

ETIOLOGY

DIAGNOSIS

IMAGE DIAGNOSIS

CLASSIFICATIONS

OVERUSE KNEE SYNDROME TREATMENT

NON SURGICAL

ANTIINFLAMATORY NON STEROIDEAL TREATMENT

INFILTRATIONS

PHYSIOTHERAPY

HIALURONIC ACID TYPES:

HYALURONIC ACID PLUS SORBITOL

EVALUATION

RESEARCH QUESTION

PROTOCOL JUSTIFICATION

HYPOTHESES

HYPOTHESIS

NULL HYPOTHESIS

OBJECTIVES

MAIN OBJECTIVE

SPECIFIC OBJECTIVES

MATERIALS

STUDY DESIGN

SELECTION CRITERIA

INCLUSION CRITERIA

EXCLUSION CRITERIA

ELIMINATION CRITERIA

VARIABLES

POPULATION UNIVERSE

POPULATION SIZE

STUDY DESIGN

STATISTICAL ANALYSIS

ETHICAL IMPLICATION

ORGANIZATION

APPENDIX 1

APPENDIX 2

APPENDIX 3

REFERENCES

Abstract:

Introduction: The presence of overuse syndrome has been found with increasing frequency in patients who perform impact sports activities. Repetitive micro-trauma as a result of intense sport will cause the onset of joint degeneration that will generate pain, functional disability and in some cases limitation to continue carrying out sports activities.

Aims: the aims of this prospective and longitudinal intervention cohort study is to evaluate the safety and efficacy of hyaluronic acid plus sorbitol through clinical and functional analysis of sports patients undergoing overuse knee syndrome.

Patients and Methods:

According to the inclusion criteria, the participants who agree to part of the study will be enrolled, two dose of hyaluronic acid plus sorbitol will be applied in each knee, then strategies techniques for continue with sports activities. The KOOS and IKDC scores will be evaluated at 15 days 3 and 6 months. Once we obtain all data results a statistical analysis will be made.

Introduction:

It is increasingly common to find patients who refer knee pain after any kind of sports, overuse syndrome of the knee has been the most common cause. This entity can be conditioned by repetition microtrauma which are in direct relation with the repenting rise of the intensity, duration and volume in sports activity, and also we could find incorrect training techniques or also do not count with appropriate equipment during training.

Knee Overuse Syndrome

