Drug treatments commonly include the use of pain relievers such as aspirin or acetaminophen, and nonsteroidal anti-inflammatory drugs (NSAIDs); The use of NSAIDs is controversial due to the absence of histological inflammatory response in knee overuse syndrome. There is also concern that NSAIDs may interfere with the normal healing response of muscles and tendons.

INFILTRATIONS

- Platelet Rich Plasma (PRP) injections have been studied for the treatment of tendinopathy and osteoarthritis, obtaining Good medium-term results in the treatment of recalcitrant patellar tendinopathy by applying multiple injections. The use of PRP has been qualified by the Clinical Practice Guidelines of the American Academy of Orthopedic Surgeons (AAOS) for the treatment of knee osteoarthritis, however their decision was that it's use cannot be recommended for or against treatment of knee osteoarthritis.

INFILTRATION WITH HIALURONIC ACID

Visco-supplementation with hyaluronic acid is one of the most recommended treatments for the non-surgical management of osteoarthritis, it can be recommended as first-line therapy, or when corticosteroids and non-steroidal anti-inflammatory drugs are inefficient, contraindicated or poorly tolerated; viscosupplementation is a safe procedure, without any systemic or local side effects, excluding possible injection pain and a feeling of heaviness for a few hours or days after treatment. Hyaluronic acid is one of the most used methods to preserve the cartilage and intra-articular structures of the knee. It protects the chondrocytes and lubricates the joint to stabilize the cartilage and the synovial membrane, benefits have also been described in its analgesic and intra-articular structures of the knee. It protects the chondrocytes and lubricates the joint to stabilize the cartilage and the synovial membrane, benefits have also been described in its analgesic and anti-inflammatory effects. Viscosupplementation significantly reduces knee pain during the first months, after which the effect is maintained for another 12 to 18 months. During this time joint function can improve and therefore patients can quickly return to sports activities.

Physiotherapy

A fundamental part of the overuse syndrome treatment is to know that mistakes in techniques of training could be avoided by guidelines of different type of exercises. Physical therapy should focus on stretching inflexible muscles and tendons (for

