To evaluate safety and efficacy of hyaluronic acid with sorbitol in athletes with overuse knee pain by comparing functional outcomes at short, medium and long term after treatment.

Specific Objectives

- To assess the safety and efficacy of hyaluronic acid with sorbitol in patients with sports-associated knee pain.
- To compare the clinical and functional results of patients with sport-associated knee pain after before and after treatment.

METHODS

Study Design

This research will be a cohort study, prospective and unidirectional direction.

Selection Criteria

- Patients with knee pain for more than 3 months
- Patients between 30 and 55 years old
- Patients without a history of previous knee joint surgery.
- Patients without chronic-degenerative diseases such as diabetes, hypertension, rheumatoid arthritis or other autoimmune diseases.
- Patients who perform impact social sports at least 3 times a week for more than 1 hour in the last 3 months prior to treatment.
- Patients without a history of allergies to non-steroidal anti-inflammatory drugs.
- Patients with no history of infection in or around the knee.

EXCLUSION CRITERIA

- Patients who cannot be categorized as social athletes.
- Patients with an associated sports injury that limits their sports practice.
- Patients who have a treatment associated with knee pain independent of that established in the study protocol.

ELIMITATION CRITERIA

- Patients who suffer from an injury or illness during the study that may limit their sports activity or who require an analgesic or anti-inflammatory treatment other than that established in the protocol.
- Patients who personally want to leave the study.
- Patients who did not have complete follow-up during the study.
- Patients who present an allergic or infectious reaction related to hyaluronic acid or prolotherapy or sepsis and antisepsis methods for infiltration.
- Patient with an allergic reaction to non-steroidal anti-inflammatory drugs.

VARIABLES

Variable	Operational Definition	Dimension	Variable type	Instrument	Indicator
Age	Time of life of any person	Without categories	Quantitative Discrete	Interview	Years
Gender	Biological and physiological characteristics that differentiate a man from a woman	Female Male	Qualitative Nominal	Interview	Gender
Body Mass Index	Score calculated by weight and height of a person.	Normal Overweight Obesity	Quantitative Discrete	Measuring tape Weighing machine	Weight in kg / Height in square meters

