Cannot perform daily activities	 0	 1	 2	 3	 4	 5	 6	 7	 8	 9	 10	No limitation in daily activities
------------------------------------	----------------------------	----------------------------	----------------------------	----------------------------	----------------------------	----------------------------	----------------------------	----------------------------	----------------------------	----------------------------	-----------------------------	-----------------------------------------

APPENDIX 2

Knee Injury and Osteoarthritis Outcome Score (KOOS)

Pain

P1 How often is your knee painful?	 Never	 Monthly	 Weekly	 Daily	 Always
------------------------------------	--------------------------------	----------------------------------	---------------------------------	--------------------------------	---------------------------------

What degree of pain have you experienced the last week when...?

P2 Twisting/pivoting on your knee	 None	 Mild	 Moderate	 Severe	 Extreme
P3 Straightening knee fully	 None	 Mild	 Moderate	 Severe	 Extreme
P4 Bending knee fully	 None	 Mild	 Moderate	 Severe	 Extreme
P5 Walking on flat surface	 None	 Mild	 Moderate	 Severe	 Extreme
P6 Going up or down stairs	 None	 Mild	 Moderate	 Severe	 Extreme
P7 At night while in bed	 None	 Mild	 Moderate	 Severe	 Extreme

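### Safety is an objective, but no contact is scheduled between the injection and day 15 and no reaction variable is named, so short-lived injection reactions are likely to be under-counted

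*Combined protocol and SAP*

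**What the plan says.** Safety appears in the study title, in the general objective and in the first specific objective: "To assess the safety and efficacy of hyaluronic acid with sorbitol in patients with sports-associated knee pain".

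The schedule after injection is given twice. The Abstract says "The KOOS and IKDC scores will be evaluated at 15 days 3 and 6 months", and the After treatment Group text under Study Design says "Scores recorded data will be made at 15 days, then at 3 and 6 months". For the first three days there is advice only: "It will be recommended to not make any kind of sports activity following the next 72 hours", together with icing. No call, diary or visit before day 15 is described.

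The Statistical analysis section names one kind of data to be followed over time: "Recorded data of the functional scores will be evaluated before and after treatment, also at 15 days, 3 and 6 months after hyaluronic acid supplementation". The Variables table lists demographics, side, athlete category, KOOS, IKDC, the injection and coaching. It has no row for reactions or adverse events.

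Reactions are mentioned in two other places. The background on hyaluronic acid infiltration calls the procedure free of side effects, "excluding possible injection pain and a feeling of heaviness for a few hours or days after treatment". The elimination criteria remove "Patients who present an allergic or infectious reaction related to hyaluronic acid or prolotherapy or sepsis and antisepsis methods for infiltration".

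**The concern.** A safety objective needs reactions to be looked for at the time they happen. The two local effects that the protocol names are short, and the first scheduled contact comes about two weeks after the injection. A final report could then state that few or no reactions were recorded when nobody had asked during the days that matter.

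Missed events can only lower the reported rate, and this is a single treated cohort, so there is no comparison group to reveal the shortfall. The elimination rule adds to the problem. It depends on someone learning of a reaction, and it then takes that participant out.

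**Working it through.** There is no stated safety figure to reproduce. The check sets the schedule, the recall windows and the stated duration of reactions side by side.

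**1. Reaction duration against first contact.** The background gives hours to days for injection pain and heaviness. Reading days as 1 to 7 (an assumption), a reaction that starts at injection ends between 15 − 1 = 14 and 15 − 7 = 8 days before the first contact.

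**2. KOOS at day 15 (Appendix 2).** The degree-of-pain items carry the stem "What degree of pain have you experienced the last week when", and the difficulty items use the same one-week period. Day 15 − 7 = day 8, so these items cover none of the first 72 hours. They are P2–P9 (8), A1–A17 (17) and Sp1–Sp5 (5), 30 of the 42 items. The other 12 (P1, Sy1–Sy7, Q1–Q4) show no one-week stem, but they ask about general knee pain, stiffness, swelling, catching and confidence, not about a reaction.

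**3. IKDC at day 15 (Appendix 1).** Items 2, 4 and 6 look back four weeks: 28 − 15 = 13 days before the injection plus 15 days after it. They do span the injection. They ask how often there was pain, how stiff or swollen the knee was, and whether it locked. In people enrolled for knee pain of more than three months, the answer cannot separate an injection reaction from the condition.

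**4. Is there an earlier visit at which to ask?** The plan speaks of two doses. The Composition text gives a 2 ml syringe with 20 mg/ml hyaluronic acid and 40 mg/ml sorbitol. Two syringes give 2 × 2 × 20 = 80 mg and 2 × 2 × 40 = 160 mg, which match the 4 ml described in one procedure. No second session is described. The Variables table also allows single- and multiple-dose categories, so the number of sessions should be reconciled across these sections.

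**5. Direction and illustrative size.** Recorded rate = true rate × share captured; chance of recording none = (1 − true rate × share)^n. Neither the true rate nor the share captured is in the documents. The table assumes a true rate of 10% and uses the planned limits of 60 and 120 participants.

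| Share captured | Recorded rate | Chance of none, n = 60 | Chance of none, n = 120 |
|---|---|---|---|
| 100% | 10% | 0.2% | <0.01% |
| 25% | 2.5% | 22% | 4.8% |
| 10% | 1% | 55% | 30% |

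For true rates of 5% to 20% and capture of 10% to 50%, the recorded rate runs from 0.05 × 0.10 = 0.5% to 0.20 × 0.50 = 10%. With zero events, the one-sided 95% upper limit is 1 − 0.05^(1/n): 4.9% for 60 and 2.5% for 120. Those limits are valid only if reactions were actually sought.

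**The case against.** **Contacts may hold more than questionnaires.** A reader might infer that nothing but scores is collected after injection. The documents do not go that far. The Variables table lists interview and physical examination as instruments for both scores, and Physical Resources under Organization mentions examination and sonography in the medical office without tying them to a visit. Appendix 3 breaks off at the treatment heading in the available text, so a reaction field cannot be excluded. Consent pages are not available either, and they may tell participants to report reactions. All of this stands. None of it adds a scheduled contact before day 15, and an examination then would not find a reaction that had resolved.

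**A coverage percentage is tempting.** Three one-week windows in about 180 days give 21/180 = 12%, which looks like the share of follow-up observed. It should not be used. The four-week IKDC items cover 15 + 28 + 28 = 71 of 180 days, about 39%, and 12 KOOS items show no one-week limit. More basically, days covered by a function score do not measure reactions captured.

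**Allergic and infectious reactions.** A reader might infer that these too are over by day 15. The documents give no onset or duration for them, and the hours-or-days statement concerns only injection pain and heaviness. Serious reactions may well be reported unprompted. The timing argument is therefore confined to short local effects.

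**The deeper gap is the missing safety endpoint.** This is fair: the general objective is framed as a comparison of functional outcomes, and no reaction endpoint is defined. But a field added at day 15 alone would still rely on memory of events up to two weeks old, so timing needs its own remedy.

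**Conclusion.** The point holds for short-lived local reactions. As written, the plan is likely to under-count them, because the first scheduled contact falls after they would usually have ended and neither score can identify them. This rests on the protocol's own statement of duration and on no earlier contact being specified in text that is unavailable.

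The direction follows from the design; the size does not. A reader might conclude that the safety result will certainly be too favourable, or by a known amount. The documents support only that it is likely to be, since unprompted reports are possible and no reaction or capture rate is given. The table above is illustration.

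For allergic and infectious reactions the conclusion has a different basis: participants who have them are eliminated. If elimination means removal from the analysis, which the protocol does not spell out, the reported safety result moves in the same favourable direction.

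**What to change.** In the After treatment Group text and Appendix 3:

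- Add a one-page dated reaction card, handed out at the injection, completed daily for the first week for each knee, and returned at the existing day-15 visit. It should cover at least pain and heaviness, plus general signs such as swelling, redness, fever and rash, with start and end dates.
- At day 15, month 3 and month 6, ask directly about reactions since the last contact, with dates.

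In the Variables table and Statistical analysis, add a reaction variable. Report the share of all injected participants with each reaction, including those later eliminated.

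The cost is one page, a wording change and a small burden on participants, with no extra visit or staff. The reported reaction rate will probably look less favourable. The card improves counting; it alerts nobody before day 15, and the questions at months 3 and 6 still rest on long recall.

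The card may come too late. Research Universe gives June to October 2022, and the document is dated 01/12/2023, which is later in either date order. If injections are complete, the report should state that early reactions were not systematically solicited and should not present the absence of recorded reactions as evidence of safety.
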